## **STUDY ENDPOINTS**

30 days and 12 months

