## **PRIMARY OUTCOMES**

### **1. Surgical site occurrence (SSO) within 30 days**

- Superficial infection
- Deep infection
- Dehiscence
- Hematoma
- Necrosis
- Non-healing wound
- Seroma

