### **2. Delayed infection or sinus within 1-12 months**

- Office removal of suture or knot
- Return to the operating room (OR) for draining wound
- Knot removal for palpability (added April 20, 2019)

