## **EXCLUSION CRITERIA**

1. No planned need for closure of deep soft tissues
2. Pregnancy
3. Age less than 1 year
4. Repair of skin or other tissues with epithelium

Indications for Use	The Mesh Suture is indicated for use in soft tissue approximation and/or ligation. Not to be used for the skin.
Patient Population	Subjects will be recruited from a population of patients treated for orthopedic conditions by [name]
Study Size and Center	N=80 patients at Wigmore Clinic Arabkir Joint Medical Center in Yerevan, Armenia
Clinical Study Design	Safety and efficacy trial of a medical device (surgical suture). Prospective, Non-blinded and non-randomized, Multi-center, Single-surgeon
Primary Safety Endpoints	Surgical site occurrence (SSO) with 30 postoperative days Delayed infection or sinus within 1-12 months
Secondary Effectiveness Endpoints	Operating room handling Rehospitalization for any wound issue within 30 days Return to the OR for any reason within 1-12 months General rating of the suture by surgeon
Study Flow	
SCREENING
 
 
1. Preoperative assessment by the surgeon to confirm that the patient meets the study entry criteria.
 
2. Informed consent obtained from patient by study staff.
 
 
SURGERY
 
 
1. Perform surgery and close deep tissues with Mesh Suture
 
2. Record intraoperative information on CRF.
 
 
PATIENTS EXCLUDED FROM FURTHER FOLLOW-UP
 
Based on the tissues, patient's condition, and all other intraoperative factors, [name] may decide not to use a mesh suture. These patients will not undergo any further follow-up nor be included in the safety and effectiveness analyses.
 
INITIAL FOLLOW-UP
 
Patient follow-up will be per [name] established protocols. All patients will be seen at least or contacted by study staff by 30 days to assess healing of the incision and assess for possible SSO.
 
FINAL FOLLOW-UP
 
Late patient follow-up will be per [name] established protocols. All patients will be seen at least or contacted by study staff by the end of the study period (12 months after the surgery) to assess healing of the incision, functional outcome of surgery, and assess for possible delayed infection.

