## **MISSING DATA**

It is the responsibility of the PI to accurately and completely fill out the CRF. Missing data will be analyzed by the data monitoring committee and completed with assistance of the PI. Follow-up either in person at the Wigmore Clinic or by telephone is the responsibility of the PI.

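### The only required SSO check is due by day 30 with no earliest date, so late events in the 30-day primary window may be missed; the 12-month wording also needs aligning with the Study Timelines section

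*Protocol*

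**What the plan says.** The protocol names its endpoint times as "30 days and 12 months". The first primary outcome is "Surgical site occurrence (SSO) within 30 days" and the second is "Delayed infection or sinus within 1-12 months".

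The contacts that should capture these outcomes are in the Study Flow table. Under Initial Follow-up: "All patients will be seen at least or contacted by study staff by 30 days to assess healing of the incision", and to look for a possible SSO. Under Final Follow-up: "All patients will be seen at least or contacted by study staff by the end of the study period (12 months after the surgery"). This last contact covers incision healing, function and possible delayed infection. Beyond these contacts, both entries leave follow-up to the surgeon's own established practice, which the protocol does not describe. The Missing Data section allows a telephone call in place of a visit: "Follow-up either in person at the Wigmore Clinic or by telephone is the responsibility of the PI".

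Four other parts bear on the point:

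- Study Timelines says that patients are followed for one year and refers to a one-year final examination.
- Adverse Events commits the investigator and sponsor to documenting and reporting all adverse events.
- The section on monitoring participant safety has data sent to the data monitoring committee every other month.
- That section and Closure of the Study both set a moratorium at an SSO rate of 15%.

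**The concern.** An outcome defined over a fixed window is fully observed only if someone looks at or after the end of the window. The Initial Follow-up rule reverses this: day 30 is the last permitted day for the check, not the first. A telephone call on day 7 or day 14 meets the rule and says nothing about the remaining 23 or 16 days.

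The error has one direction. A check made too early can miss events but cannot add any. The Safety and Effectiveness section rests the safety conclusion on comparison with historical controls, so an understated SSO rate favours the new suture. The same rate drives the 15% moratorium, a participant safeguard in a study that the protocol calls first-in-human and that admits children. Several SSO components, such as a superficial infection treated with oral antibiotics or a seroma, could occur without the patient returning to the surgeon, so asking the patient matters.

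**Working it through.** The protocol gives no figure that depends on contact timing, so there is nothing of its own to reproduce. The check is first textual, then illustrative.

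**Text, 30-day outcome.** The window is day 0 to day 30. The required check falls on any day up to day 30. No other section fixes an assessment on or after day 30. The Study Endpoints line names the time point but schedules nothing. The rule therefore permits incomplete observation of the window.

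**Text, 12-month outcome.** The window is month 1 to month 12. Final Follow-up again gives only a latest date. Study Timelines, however, states one year of follow-up and a one-year final examination. A patient last contacted in month 8 would satisfy the first passage but not the second. The fault here is a mismatch in wording.

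**Illustration, SSO moratorium.**

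Inputs from the protocol: n = 80 and a threshold of 15%. Applied to the full sample, 0.15 × 80 = 12 events.

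Assumptions not in the protocol: a true SSO rate p of 18%; a share L of SSOs arising after the contact; all of those events lost.

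Recorded rate = p × (1 − L). Chance of recording at least 12 events = P(X ≥ 12), with X ~ Binomial(80, p × (1 − L)).

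| L | Recorded rate | Expected recorded events | P(X ≥ 12) |
|---|---|---|---|
| 0 | 18.0% | 14.4 | 0.80 |
| 5% | 17.1% | 13.7 | 0.73 |
| 10% | 16.2% | 13.0 | 0.66 |
| 20% | 14.4% | 11.5 | 0.49 |
| 35% | 11.7% | 9.4 | 0.22 |
| 50% | 9.0% | 7.2 | 0.05 |

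**Second illustration, by contact day.** Assume instead that SSOs are spread evenly over 30 days, that the contact is the only source of events, and that the true rate is 15% (12 of 80 expected). Share of window covered = contact day / 30. Expected events missed = 12 × (1 − share).

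| Contact day | Share covered | Expected events missed | Recorded rate | P(X ≥ 12) |
|---|---|---|---|---|
| 30 | 100% | 0 | 15.0% | 0.55 |
| 21 | 70% | 3.6 | 10.5% | 0.13 |
| 14 | 47% | 6.4 | 7.0% | 0.01 |
| 7 | 23% | 9.2 | 3.5% | <0.001 |

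Both tables are upper bounds on the loss for their inputs, because they allow for no recovery of late events. Both also count events at the full sample of 80. The protocol describes an early moratorium, which would have to act during accrual, so these probabilities show sensitivity and not how the rule would run.

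**The case against.** A reader might infer that events after an early contact go uncounted and that those patients are classed as event-free. The protocol does not say so. It defines the outcome by when the SSO occurs, not by what is seen at the contact, so a day-20 event learned of later is still an SSO. There are several other routes of capture:

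- Documentation of all adverse events.
- Review of all complications, with data going to the data monitoring committee every other month.
- Recording of results through routine practice.
- A separate outcome for 30-day rehospitalization for wound issues.
- Access to the medical record.
- A later contact that again assesses the incision.

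The required contact is also a minimum on top of a surgeon's schedule that we cannot see, and that schedule may include a visit after day 30. This stands, and it limits the claim to events that *may* be missed. It does not remove the point. Those routes handle events that come to someone's attention; none requires the patient to be asked at or after day 30, and the final contact is directed at delayed infection rather than early SSOs.

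A reader might also infer that both primary outcomes share the defect equally. They do not, because Study Timelines largely answers the 12-month half.

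Finally, the magnitudes rest on a true rate and a late share that have no source in the protocol. That is correct, and small late shares have small effects: 0.73 against 0.80 at a 5% loss. How to classify incompletely observed patients in the analysis is commonly left to the SAP, so its absence is not part of this point.

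**Conclusion.** The point holds for the 30-day SSO outcome. The only fixed check has a latest date and no earliest date, so a compliant contact can leave part of the primary window unobserved. Events after it may be missed, and any such loss lowers the SSO rate used for the historical comparison and the 15% moratorium. For the 12-month outcome, the conclusion is only that Final Follow-up is worded more loosely than Study Timelines and that the two should agree.

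The actual size is unknown, since it depends on when contacts are made, when SSOs arise and how many are recovered by other routes. A fall in the chance of reaching 12 of 80 from 0.80 to 0.49 is an upper bound for an assumed true rate of 18% with 20% of events arising after the contact. It is not an estimate for this trial. The change is worth making because it removes a bias in one direction at little cost.

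**What to change.** In the Study Flow table:

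- **Initial Follow-up:** set the first outcome contact on or after day 30, with a short window (for example day 30 to 37).
- **Final Follow-up:** set the final contact at or after month 12, with a short window, so that it matches the one-year examination in Study Timelines.
- **Content of each contact:** ask about every listed event since the previous contact, with the date of each event, and record the date of the contact itself.
- **Reporting:** state how many patients were not observed to the end of each window.

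Earlier visits under the surgeon's usual practice can stay as they are. The cost is a change of wording, a slightly later contact and possibly one extra telephone call for patients whose routine visits end before day 30. The reported SSO rate may rise slightly, and some patients may be shown as incompletely observed.

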## **PATIENT SELECTION**

Will be at the discretion of the PI, with patients matching inclusion criteria and not have any exclusion criteria. The patient should be able to have postoperative follow-up visits and have the appropriate guardians to provide consent if under the age of 18.

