## **INCLUSION CRITERIA**

Consecutive patients undergoing planned surgery at the Wigmore Clinic and Arabkir Joint Medical Center in Yerevan, Armenia, and requiring deep soft tissue approximation and/or ligation:

1. Age: more than 1 year
2. Gender: male or female
3. Indications for use: tendon lengthening, ligamentoplasty, tendon repair, repair of joint capsules, other deep tissue approximations

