**CONSENT PROCESS**

The consent will be obtained by the attending surgeon, or by the study coordinator. This will occur preferably in the clinical office of the attending, but also in the preoperative holding area before surgery. We expect the consent process to take 10 minutes. Suture examples will be shown to the

patient. Steps taken to minimize coercion or influence will be contained in the consent form. Consent will be obtained by native Armenian speakers.

All patients who meet inclusion criteria and who do not have exclusion criteria will be approached for consent, so long as their legal guardian or legal representative is present and consents to the orthopedic procedure.

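### Patient Selection leaves the choice among eligible patients to the PI, which conflicts with the consecutive, all-approached series stated elsewhere and opens the historical comparison to selection bias of unknown size and direction

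*Protocol*

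**What the plan says.** The protocol states the enrolment rule in three places.

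- Inclusion Criteria: "Consecutive patients undergoing planned surgery at the Wigmore Clinic and Arabkir Joint Medical Center in Yerevan, Armenia".
- Consent Process: "All patients who meet inclusion criteria and who do not have exclusion criteria will be approached for consent", with the added condition that a guardian or legal representative is present and consents to the operation.
- Patient Selection: "Will be at the discretion of the PI, with patients matching inclusion criteria", and with no exclusion criterion present. This section adds two conditions: the patient can attend follow-up, and minors have a guardian who can consent.

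A second selection step comes later. The Study Flow row of the summary table, after the Exclusion Criteria, says: "Based on the tissues, patient's condition, and all other intraoperative factors, [name] may decide not to use a mesh suture". It continues: "These patients will not undergo any further follow-up nor be included in the safety and effectiveness analyses".

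The same table gives the design as "Prospective, Non-blinded and non-randomized, Multi-center, Single-surgeon". Safety and Effectiveness sets the aim of outcomes at least as good as current surgical care and takes historical controls as the comparator for both safety and efficacy. The section on increased risks says that each hospital's SSO rate reflects its procedures and its patients. Number of Local Participants expects up to 100 consented patients to yield 80 who may receive the device.

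**The concern.** A consecutive series in which every eligible patient is approached leaves the surgeon no choice among eligible patients before consent. A discretionary series does. Staff cannot follow both rules as written.

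The conflict matters more here than in a randomised trial, where selection before randomisation affects both arms alike. In this study the only comparator is external, so any difference in case mix between the treated series and the historical patients passes straight into the comparison. Eligibility is broad (anyone over 1 year, several tendon, ligament and capsule procedures, and other deep tissue closures), so risk among eligible patients may vary a good deal. Under Observation and Recording of Results, the PI and designees also record the outcomes. The protocol calls for no record of eligible patients who were never approached, so a reader of the final report could not judge how far selection had operated.

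**Working it through.** **Can the three statements be reconciled?**

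1. Inclusion Criteria and Consent Process agree: consecutive patients, all eligible patients approached.
2. Patient Selection applies discretion to patients who already match the criteria. It is therefore a further filter and not a restatement of them.
3. Confirmation of eligibility has its own step, the surgeon's preoperative assessment under Screening in the Study Flow row. The word discretion is not needed for that step.
4. No section limits the discretion or says which rule prevails.

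**Is there a figure in the plan to reproduce?** No. The protocol gives no historical SSO rate, margin, alpha or power. The only relevant counts are 80 treated from up to 100 consented, so up to (100 − 80)/100 = 20% of consented patients may not receive the device. Those figures do not cover patients who were never approached.

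**How large could the effect be?** This can be shown only under assumptions. Assume an all-comer SSO rate of 10%, a highest-risk group making up 20% of eligible patients, and a risk in that group of k times the rate r in the rest, with k = 2 or 3.

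- All-comer rate: 0.8r + 0.2kr = 0.10, so r = 0.10 / (0.8 + 0.2k).
- k = 2: r = 0.10/1.2 = 8.3%.
- k = 3: r = 0.10/1.4 = 7.1%.

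If that whole group is passed over, the enrolled rate equals r. The shift is 10 − 8.3 = 1.7 points or 10 − 7.1 = 2.9 points in favour of the device.

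**The reverse case.** With the same inputs, suppose the 20% of eligible patients who are passed over all come from the lower-risk 80%. The enrolled rate is (0.6r + 0.2kr)/0.8.

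- k = 2: (0.6 × 8.33 + 0.2 × 16.67)/0.8 = 10.4%.
- k = 3: (0.6 × 7.14 + 0.2 × 21.43)/0.8 = 10.7%.

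The shift is 0.4 to 0.7 points against the device.

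**Effect on the 15% SSO moratorium** (Closure of the Study). Read the threshold as 12 of 80 at full accrual. The binomial chance of 12 or more events is 0.10 at a rate of 10%, 0.03 at 8.3% and 0.01 at 7.1%. If 20% of eligible patients are high-risk with a 35% rate and the rest have 10%, the all-comer rate is 0.2 × 35 + 0.8 × 10 = 15%. The chance then falls from 0.55 with all comers to 0.10 if every high-risk patient is omitted.

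**The case against.** The strongest reply is that discretion here means only the PI's judgement that a patient fits. Patient Selection ties it to the entry criteria and then lists two matters that do need judgement: follow-up and guardianship. The Consent Process repeats the guardian condition. On that reading the sections fit together and only the wording needs tidying. The reading is possible but fits poorly, because the discretion covers patients who already meet the criteria and eligibility is confirmed elsewhere. It would be settled by the same edit.

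Other parts of the reply stand.

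- A reader might infer that the surgeon will pick lower-risk patients. The text permits this but does not show that it is intended. Directions for Use points towards tissues at risk of pull-through or tearing, which could favour harder repairs. The direction is unknown.
- A reader might infer that the historical rates come from unselected patients. The protocol names no source, rate or population for them.
- The illustrated shift is an assumed extreme, with the whole highest-risk fifth omitted, and it is small beside sampling error. At 10% and n = 80 the standard error is √(0.1 × 0.9/80) = 3.4 points, with a 95% half-width of about 6.6. That limits what the illustration proves, although bias, unlike sampling error, does not shrink with more patients.
- A screening log may be kept in site documents, and consent forms and case report forms will trace the step from consent to implant. The gap is clearest for eligible patients never approached.
- Removing the discretion before consent leaves the intraoperative decision as a second route of selection.

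**Conclusion.** The conflict is real and should be resolved. The protocol gives two enrolment rules, and the discretionary one would allow case selection that the described records could not reveal, in a single-surgeon study whose claims rest on historical controls and whose primary safety outcome depends on case mix. The result is a comparison open to selection bias of unknown size and direction. It would favour the device if higher-risk patients were passed over, by 1.7 to 2.9 points under the assumed inputs (10% all-comer rate, highest-risk 20% omitted, two to three times the risk of the rest).

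It would go too far to say that the historical comparison loses its basis because of this wording. No decision is shown to change, since the protocol states no historical rate or margin, and the comparison is already weak for that reason.

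**What to change.** In Patient Selection, delete the words that leave the choice to the PI and state the single rule of the Inclusion Criteria and Consent Process: every consecutive eligible patient is approached. Keep the follow-up and guardian conditions, but as listed eligibility criteria.

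Add a log of patients who are eligible, approached, consented and implanted, with the reason for each loss. Include patients in whom the surgeon decides during surgery not to use the device, and report the log beside the primary outcomes. The log leaves intraoperative judgement untouched and makes that step visible, although it gives no outcomes for those patients.

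Cost: a wording amendment, a small amount of record keeping by existing staff, and a slight loss of flexibility for the PI. No extra patients or visits are needed.

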## **SAFETY AND EFFECTIVENESS**

This safety and effectiveness study is intended to demonstrate that overall patient outcomes are no worse than or adversely different from the current surgical standard of care. In addition to overall patient outcomes, the study will also examine adverse outcomes related to the use of the suture.

An overarching issue is that the suture used in the procedure reflects only a small part of the total treatment of the patient – including what adverse occurrences are responsible for surgical morbidity and mortality. Robust evaluation of suture closures is best assessed in the setting of an animal study where the surgical wound can be opened and tested at the end of the follow-up period. This then allows the investigator to readily inspect the suture line and assess the abdominal suture closure for safety and effectiveness endpoints including suture pull-through. This is not possible in the treatment of humans. Therefore, safety is best noted by the achievement of standard wound healing rates and the absence of delayed infections in comparison to historical controls. Efficacy is best noted by the achievement of standard functional outcomes in comparison to historical controls.

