### **CLOSURE OF THE STUDY**

For this first-in-human use of mesh suture, 80 cases will be performed in this safety and effectiveness study. The hypothesis is that the mesh suture will be equivalent in performance to standard suture. The study will be closed upon accrual of 80 patients, final follow-up of these patients. An early moratorium of the study will occur with a 15% rate of SSO, or 3 early and unexpected dehiscences of deep tissue closure attributable to the suture as judged by the data monitoring committee. Early closure of the study will occur based on the judgement of the PI, the sponsor, and an early demonstration of equivalence to the results of standard suture as judged by a lack of early and late infections and appropriate postoperative surgical results demonstrating appropriate tissue approximation for internal load-bearing closures.

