**POTENTIAL RISKS TO PARTICIPANTS**

The Mesh Suture will be manufactured (fabrication, sterilization and packaging) using GMP standards by one of the largest suture companies in the world, Surgical Specialties. The risk of contamination or inadequate preparation is very low considering the experience of the manufacturer. This will minimize the risk of an issue with the suture itself (sterility, composition, tensile characteristics, etc.) to the patient.

The overwhelming majority of risks to the patient is inherent to surgery and the surgical process, and is not relatable or attributable to the suture used for closure. The risks of surgery as delineated in this submission far outweigh any ADDED risks of using Mesh Suture for closure as opposed to standard suture. There are risks of the use of a permanent suture in terms of delayed infection.

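### Late safety is judged by an absence or lack of delayed infections, which is neither a workable test of no worse than standard nor, when met in 80 patients, evidence of equivalence

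*Protocol*

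**What the plan says.** Delayed infection or sinus between 1 and 12 months is one of two primary outcomes (Protocol, Primary Outcomes). The study is described as "Prospective, Non-blinded and non-randomized, Multi-center, Single-surgeon", and the Closure of the Study section states that "80 cases will be performed in this safety and effectiveness study". There is no concurrent control.

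The aim, under Safety and Effectiveness, is to show that "overall patient outcomes are no worse than or adversely different from the current surgical standard of care". Closure of the Study puts it as a hypothesis: "The hypothesis is that the mesh suture will be equivalent in performance to standard suture".

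Two sentences say how late infection bears on that aim:

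- Safety and Effectiveness: safety is best noted by standard wound healing rates and by "the absence of delayed infections in comparison to historical controls".
- Closure of the Study: the study may close early on a demonstration of equivalence "as judged by a lack of early and late infections", together with appropriate postoperative surgical results.

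The protocol also accepts that the expected rate is not zero. Potential Risks to Participants states: "There are risks of the use of a permanent suture in terms of delayed infection". Compensation for Research-Related Injury lists delayed infection among risks that come with any surgical suture.

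No historical rate of delayed infection, margin or numeric limit is given for this outcome. By contrast, a 15% limit is given for surgical site occurrence.

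**The concern.** A target of none and a target of no worse than standard are different standards once the standard rate is above zero. Taken at its word, the first can fail a suture that is exactly as safe as the comparator. The opposite error needs no literal reading: a count of zero in a small single-arm series leaves a range of true rates open, so it cannot by itself carry a claim of equivalence. The early-closure sentence makes this practical, because there a lack of infections is an element of declaring equivalence, possibly on fewer than 80 patients or with incomplete 12-month follow-up.

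At stake is how a primary safety outcome is interpreted. One or two delayed infections could be taken as failure, or none as proof, and neither conclusion would follow from the data.

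**Working it through.** **Inputs**

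- n = 80, single arm (Protocol, Closure of the Study). All patients are taken as evaluable at 12 months, which is the favourable case.
- True delayed-infection rate p: not in the protocol. It is assumed here over a range of 0.1% to 5%.
- The protocol derives no sample size and states no error rate, margin or event rate, so there is no figure of its own to reproduce.

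**Step 1. How often would an equally safe suture miss a literal zero-event criterion?**

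P(at least one event) = 1 − (1 − p)^80

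| Assumed true rate p | P(0 events) | P(at least 1 event) |
|---|---|---|
| 0.1% | 92.3% | 7.7% |
| 0.5% | 67.0% | 33.0% |
| 1% | 44.8% | 55.2% |
| 2% | 19.9% | 80.1% |
| 3% | 8.7% | 91.3% |
| 5% | 1.7% | 98.3% |

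(At 1% the unrounded value is 0.5525; it is quoted as 55% elsewhere.)

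The break-even rate, where missing and meeting are equally likely, is 1 − 0.5^(1/80) = 0.86%.

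**Step 2. Do the protocol's own data place p?**

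Only loosely. The first clinical series in the supporting literature (mesh strips, abdominal wall defects) reports one knot removed in the office among 107 patients: 1/107 = 0.93%, exact 95% CI 0.02% to 5.1%. The second (mesh strips, contaminated hernias) reports no delayed suture sinus in 48 patients, with an exact two-sided upper limit of 7.4%. Putting these rates into the formula of Step 1:

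- 1/107 gives a 52.8% chance of at least one event in 80.
- Pooled, 1/155 = 0.65% gives 40.4%.

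These fall on either side of break-even. They also concern a different device and different surgery, and not standard suture, so they do not settle the baseline.

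**Step 3. What does zero of 80 establish?**

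This step needs no assumed baseline. The exact upper limit for 0/n is 1 − α^(1/n).

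- One-sided 95%: 1 − 0.05^(1/80) = 3.7%
- Two-sided 95%: 1 − 0.025^(1/80) = 4.5%

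With fewer patients the limits rise:

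| Evaluable patients, 0 events | One-sided 95% | Two-sided 95% |
|---|---|---|
| 80 | 3.7% | 4.5% |
| 72 (10% lost, illustrative) | 4.1% | 5.0% |
| 40 (early closure, illustrative) | 7.2% | 8.8% |

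**Step 4. What would a ceiling on the confidence limit demand?**

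Exact two-sided 95% upper limits for 80 evaluable patients, with the chance of seeing no more than that many events at an assumed true rate of 2%:

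| Events | Upper limit | P(this many or fewer) at p = 2% |
|---|---|---|
| 0 | 4.5% | 20% |
| 1 | 6.8% | 52% |
| 2 | 8.7% | 78% |
| 3 | 10.6% | 92% |

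A ceiling below 4.5% cannot be met with any result. A ceiling between 4.5% and 6.8% can be met only with zero events, which brings back the problem of Step 1.

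**The case against.** The strongest reply is that the protocol sets no zero-event rule. The phrase goes on to invoke historical controls, and a bare count of none would need no such comparison, so it can fairly be read as no excess over the historical rate. It is introduced as the way safety is best noted, within an explanation of why human suture lines cannot be inspected. No passage says that a single delayed infection means failure, and the numeric triggers in the protocol concern surgical site occurrence and dehiscence. This stands, and the literal reading is therefore only one of two. Against the milder reading, the same sentence holds wound healing to standard rates but delayed infection to absence, and the early-closure wording speaks of a lack of infections with no historical rate attached. The text does not decide between the two.

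A reader might also infer that an equally safe suture would usually fail. The documents do not support that without a condition. It is true only above a rate of about 0.86%, the protocol gives no baseline, and its nearest data lie on both sides.

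Finally, interval methods and acceptance limits are commonly left to the statistical analysis plan, which is not shown. Their absence is not the point made here. The point is the standard that the protocol does state, in two places, which a later plan would have to contradict or work around.

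**Conclusion.** The concern holds in a limited form. The protocol words the standard for a primary safety outcome as absence or lack of events, which does not match its aim of being no worse than, or equivalent to, standard suture, given a risk it acknowledges to be above zero.

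Two results follow, of different strength. The firm one does not depend on the reading of the phrase or on any baseline: zero events in 80 excludes only true rates above 3.7% (one-sided) or 4.5% (two-sided), and less if patients are lost or the study closes early. Whether that is good enough cannot be judged without a reference rate or margin, so a zero count alone does not show equivalence. The conditional one applies to the literal reading: an equally safe suture would miss the standard 33%, 55% or 80% of the time at assumed true rates of 0.5%, 1% or 2%. All figures treat patients as independent and, unless stated, all 80 as evaluable.

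It would go too far to say that the protocol fixes a formal rule under which one event means failure. The correction should be made before analysis because it affects how a primary outcome is interpreted.

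**What to change.** In Safety and Effectiveness, replace "the absence of delayed infections in comparison to historical controls" with: *a delayed infection or sinus proportion, reported with its exact 95% confidence interval, whose upper limit lies below a maximum acceptable rate justified from the historical controls and fixed before analysis*. This keeps the historical comparison and gives it a function.

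In Closure of the Study, bring "as judged by a lack of early and late infections" into line with the same criterion, so that a low or zero count alone is not called equivalence.

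Beside the criterion, state what 80 evaluable patients can support: the two-sided upper limit is 4.5% with no events and 6.8% with one. A ceiling below 4.5% is therefore unattainable, and one between 4.5% and 6.8% is again a zero-event rule. Tolerating two events would need a ceiling above 8.7%. If such a ceiling is not acceptable, the outcome is better reported as an estimate with its interval and without a claim of equivalence.

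The cost is a few sentences, with no change to visits, procedures or sample size. The real price is that the sponsor must name and defend a ceiling, and that the resulting claim is less favourable than absence or equivalence.
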